1. BACKGROUND

1.1 Epidemiology and burden of the condition

Out-of-hospital cardiac arrest (OHCA) is an important cause of morbidity and mortality in the UK. Of the 28,000 treated OHCA events in the UK each year, less than 10% of patients survive to leave hospital.[1] The Government has established a high-level strategic target to reduce OHCA mortality by 1,000 patients per year.[2]

Following cardiac arrest, immediate treatment with cardiopulmonary resuscitation (CPR) is essential to optimise the likelihood of survival.[3] Prior to ambulance arrival, CPR may be delivered by a member of the public. If that bystander has not previously received training in CPR, instructions on how to perform CPR may be provided by the ambulance dispatcher over the telephone.

The quality of CPR, defined by the depth, rate and pauses in chest compressions, is an important determinant of survival following OHCA, but even in trained rescuers, the delivery of CPR often fails to adhere to evidence-based guidelines.[4-12] Chest compression depth is a key CPR quality metric.[5, 6, 13] In a large North American observational of over 9,000 OHCA patients found that each 5-mm increase in chest compression depth was associated with improved hospital survival (odds ratio 1.05 (95% confidence interval 1.00 to 1.08, p=0.045).[5] However, it is also recognised that a chest compression depth should not exceed 6cm as compressions deeper than this provide no additional benefit, whilst increasing the risk of injury.[5, 14]

Across international guidelines, there is variation as to the terminology used in relation to the target depth of chest compressions. Most international guidelines (e.g. UK, European, USA, Australian), as shown in table one.

Table 1: Summary of terminology differences in international resuscitation guidelines

European	"chest compressions should be at least 5cm but not more than 6cm"[15]
UK	"press down on the sternum to a depth of 5–6 cm" [16]
USA	"Perform chest compressions to a depth of at least 2 inches or 5 cm for an average adult, while avoiding excessive chest compression depths (greater than 2.4 inches or 6 cm)"[17]
Australia	"The lower half of the sternum should be depressed approximately one third of the depth of the chest with each compression. This equates to more than 5cm in adults"[18]
Asia	"The depth of compression should be approximately 5 cm"[19]

Previous work has highlighted that the terminology used in the instruction to deliver CPR may affect performance. In a randomised controlled trial of 332 lay persons using a model of dispatched-assisted CPR on a manikin, participants instructed to "push as hard as you can" delivered deeper chest compressions than those instructed to "push down firmly two inches" (36.4 mm (SD 11.6) v 29.7 mm (SD 10.2), p<0.001).[20] In a similar study using a paediatric model, the instruction to "push as hard as you can" resulted in deeper chest compressions, compared with "push down approximately 2 inches" (43 mm (SD 1) v 36 mm (SD 1), p<0.01).[21]

Other chest compression depth terminology has been described in public-facing documents. In particular, the British Heart Foundation's campaign led by footballer Vinnie Jones encouraged rescuers to "compress hard and fast."

1.2 Research question

In adults delivering CPR, does the use of a specific terminology (at least v approximately v hard and fast) to instruct CPR instructions affect CPR quality?

1.3 Need for a trial

There is current uncertainty regarding the most effective terminology to use when instructing bystanders to deliver CPR, with evidence of variability in terminology across international guidelines. There is the opportunity to optimise delivery of bystander through more effective instruction.

In 2015, the International Liaison Committee on Resuscitation published a review of resuscitation science. This study will help to answer two key identified knowledge gaps, namely the optimal instruction sequence for coaching callers in telephone-assisted CPR and the impact of language barriers to telephone-assisted CPR performance.

The DIRECT study will address these knowledge gaps in a three-armed (approximately v at least v hard and fast) randomised controlled manikin trial, in which lay people will be instructed as to how to deliver CPR to a manikin. The specific terminology selected for the trial is based on that described in international guidelines and CPR publicity campaigns.

1.4 Ethical considerations

The trial will be conducted in conformance with the principles of the Declaration of Helsinki and to MRC Good Clinical Practice (GCP) guidelines. It will also comply with all applicable UK legislation. All data will be stored securely and held in accordance with Data Protection Act 1998.

This trial does not raise any significant ethical issues. Participants will give informed consent prior to participation and there is minimal risk associated with participation.

1.5 CONSORT

The trial will be reported in line with the Consolidated Standards of Reporting Trials statement.[22]

1.6 Assessment and management of risk

The trial intervention consists of participants performing 2-minutes of CPR whilst kneeling on the floor. Some people may find this tiring and it may cause discomfort in the upper limbs and knees, but such effects will be short-term. We will exclude potential participants that have a physical

disability that prevents delivery of CPR for 2 minutes while kneeling on the floor. As such, there is minimal risk associated with study participation.

2. TRIAL DESIGN

2.1 Trial summary and flow diagram

The DIRECT study is a three-armed single-centre randomised controlled manikin trial which will evaluate the effect of CPR delivery instruction terminology on CPR quality delivered by people without recent practical CPR training.

Following informed written consent, participants will be randomised in a 1:1:1 ratio to receive one of three CPR instructions and deliver two minutes of chest compressions to a manikin. There will be no follow-up.

The primary outcome is chest compression depth. Secondary endpoints will include other CPR quality metrics.

A trial summary is shown as figure one

[figure not shown]

Figure 1 Trial flow diagram

2.2 Aims and objectives

2.2.1 Primary objective

The primary objective of this trial is to assess the impact of CPR instruction terminology on chest compression depth.

2.2.2 Secondary objective

The secondary objectives of the trial are to assess the impact of CPR instruction terminology on other CPR quality metrics.

2.3 Outcome measures

The outcome measures selected for this study are key CPR quality metrics that are associated with outcome in cardiac arrest. We will also record other outcomes that may influence any choice of terminology in international guidelines.

2.3.1 Primary efficacy outcomes

The primary outcome is mean chest compression depth measured during the CPR quality assessment.

2.3.2 Secondary efficacy outcomes

The secondary outcomes are:

- Chest compression rate (min^{-1})
- Chest compression count
- % of chest compressions in target rate range (100-120 compressions per minute)
- % of chest compressions in target depth range (50-60mm)
- % delivery of good quality CPR over two-minute study period (defined as mean CPR depth in target range (50-60mm), chest compression rate in target range (100-120 compressions per minute, and with full recoil)

2.4 Eligibility criteria

Persons at NHS hospital sites are eligible to be included in the trial if they meet the following criteria:

2.4.1 Inclusion criteria

1. Provision of written informed consent
2. Aged over 18 years

2.4.2 Exclusion criteria

1. Physical disability that prevents delivery of CPR for 2 minutes while kneeling on the floor,

2. Previous participation in DIRECT study,
3. Received practical CPR training in the last 2-years,
4. Non-English speaking (to ensure that the information is standardised between groups)
5. NHS employee working in a clinical role.

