2.5 Participant identification / Screening

Potential participants will be identified and approached at research sites. Potential sources of participants include NHS administrative and ancillary staff, patients waiting for outpatient appointments, and hospital visitors.

Different approaches are envisaged for different groups of people.

Trust staff will be informed that the study is taking place by email, and administrative offices will be visited to provide study information. Staff will be notified when they can undertake the CPR quality assessment. On arriving to undertake the CPR quality assessment, eligibility will be assessed and they will be asked to sign the informed consent form.

For other groups, research staff will identify an appropriate location to undertake the CPR quality assessment on recruitment days. People passing by or waiting in the nearby area will be approached and informed that the study is being undertaken. Staff may also be recruited by this route.

Any member of research staff that has delegated authority by the principal investigator may assess participant eligibility.

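### The only health-related exclusion screens for inability to do two minutes of kneeling CPR, not for people who can do it but for whom the effort may be inadvisable, yet section 1.6 rests its minimal-risk conclusion mainly on it

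*Protocol*

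**What the plan says.** Four parts of the Protocol bear on this point.

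- **Eligibility (2.4.1, 2.4.2).** Inclusion needs written consent and "Aged over 18 years"; there is no upper age limit. Of the five exclusions, only the first concerns health: "Physical disability that prevents delivery of CPR for 2 minutes while kneeling on the floor". The other four cover earlier participation, recent practical CPR training, language and clinical NHS employment.
- **Risk assessment (1.6).** The task is described as follows: "The trial intervention consists of participants performing 2-minutes of CPR whilst kneeling on the floor". The expected effects are these: "Some people may find this tiring and it may cause discomfort in the upper limbs and knees, but such effects will be short-term". The section then restates the first exclusion and closes: "As such, there is minimal risk associated with study participation".
- **Recruitment (2.5).** Besides administrative and ancillary staff, the named sources are "patients waiting for outpatient appointments, and hospital visitors". People in these groups are approached on recruitment days while passing or waiting nearby. On who checks eligibility: "Any member of research staff that has delegated authority by the principal investigator may assess participant eligibility".
- **Baseline data (3.1, Table 2).** The variables given as examples are age, gender, height, weight, previous CPR training and previous resuscitation use. Medical history is not among them, but the list is illustrative.

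**The concern.** Being unable to do a task and being at risk from doing it are different things. The exclusion removes people in the first position. It is silent on people who can kneel and compress for two minutes but have a health reason not to exert themselves. Section 1.6 nevertheless moves from this exclusion to a statement about risk, so the conclusion goes further than the criterion can carry.

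The recruitment plan makes the gap worth closing. Some participants will be patients attending hospital for a health reason, approached on the day and checked by any delegated member of staff. In that setting the written criterion is the main screen, and staff applying it have no written ground to decline someone who could do the task but perhaps should not. What is at stake is participant safety and the soundness of the risk statement, not the statistical comparison.

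**Working it through.** The Protocol gives no figure for this risk, so there is none to reproduce. The check is whether the sections, read together, support the conclusion drawn in section 1.6.

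**Step 1: sort potential participants by what the criteria test.** Take adults who consent and meet none of the other four exclusions.

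| Person | First exclusion applies? | Eligible as written? |
|---|---|---|
| Cannot do two minutes of kneeling CPR because of a physical disability | Yes | No |
| Can do it, with no health reason against the effort | No | Yes |
| Can do it, but has a health reason against the effort | No | Yes |

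The second and third rows are treated alike. No criterion in 2.4.1 or 2.4.2 separates them.

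**Step 2: trace the argument in 1.6.** It has three supports: the expected effects are tiredness and limb or knee discomfort; these are short-term; and people prevented by disability are excluded. The first two describe what is expected in someone for whom the effort is acceptable. The third removes the first row of the table. None deals with the third row. The exclusion comes immediately before the conclusion and is its main support, though not its only one, because the short duration of the effects is also relied on. Section 1.4 also asserts minimal risk but adds no reasoning.

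**Step 3: compare 1.6 with the population in 2.5.** Section 2.5 names outpatients as a source. Section 1.6 does not mention them or say how an outpatient's health is taken into account.

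**Step 4: look for the missing screen elsewhere.**

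- Section 2.6 provides a verbal explanation, written information, time for questions and the right to withdraw. Nothing in it asks the person to consider whether the effort is safe for them.
- Section 2.8.1 places a researcher in the room, but questions during the scenario are answered by referring the participant back to the recording.
- Sections 4.1 and 4.2 record and report adverse events, which operates after the exposure.
- Table 2 names no medical history.

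These measures reduce the consequences of the gap but do not fill it.

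**Step 5: size.** Planned exposure is 330 people for about two minutes each: 330 × 2 = 660 minutes, or 660 / 60 = 11 hours in total. The number of outpatients among the 330 is not stated, nor is any event rate, so an expected number of events cannot be calculated. The short exposure suggests that it is small.

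**The case against.** The strongest reply is that the Protocol is consistent. Sections 1.6 and 2.4.2 state the same exclusion, and 1.6 does consider effort, since it says the task may be tiring. Drawing the criterion wider is then a preference, and no material risk has been shown. It is right that the two sections do not contradict each other and that no level of risk can be demonstrated. What stands is narrower: a criterion about ability is used to support a conclusion about safety, and the step does not follow for people who are able but at risk.

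A reader might infer several stronger things, which the Protocol does not support.

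- **That a site would be obliged to enrol such a person.** Section 2.4 says that people meeting the criteria may be included. That is permission, and participation is voluntary throughout.
- **That the exclusion is the only safety measure.** It is the only health-related eligibility screen. Consent, withdrawal at any time, a researcher in the room and adverse event reporting also protect participants.
- **That participants or the ethics committee were given an unsupported assurance.** The participant information sheet and the ethics application are not available, so what they say about effort or health is unknown. A health question could also appear on a case report form not yet developed when the Protocol was written.
- **That relevant conditions are common among those recruited, or that one question would prevent an event.** The clinics are not named, outpatients are one of three sources, and the Protocol has no data on either matter.

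It can also be objected that a wider exclusion comes close to a clinical rule and, if vague, leaves a medical judgement to lay people or delegated staff. That is a fair caution about wording. It is met by leaving the content of the question and any threshold to the investigator.

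**Conclusion.** The point holds in limited form. The first exclusion covers inability only. Section 1.6 relies mainly on it to call the risk minimal, names only minor short-term effects, and takes no account of the outpatients whom section 2.5 recruits. A person who can do the task but for whom the effort may be inadvisable passes every written criterion and may be enrolled.

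The likelihood of harm cannot be judged from the Protocol and is probably small. There is no effect on the sample size, the analysis or the validity of the comparison between arms. This is a cheap improvement to participant safety and to the reasoning in the Protocol, not a defect that undermines the trial.

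The conclusion assumes that the eligibility criteria are complete as written and that no unseen site document or form adds a health check. If one does, the remaining work is to refer to it in sections 1.6 and 2.4.2.

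**What to change.** Reconcile sections 1.6, 2.4.2 and 2.5.

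1. In 1.6, name exertion as a risk, acknowledge that outpatients are among those approached, and refer to the revised criterion as the way this risk is handled.
2. In 2.4.2, widen the first exclusion from inability alone so that it also covers a self-reported health reason not to undertake the effort.
3. Apply it through one question at the eligibility check, before randomisation. The content of the question and any clinical threshold are for the investigator to set; none is proposed here.
4. Add the reason to the screening log in 5.4, which already records non-participation against the exclusion criteria.

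The cost is one reworded criterion, one question, a few more screen failures (mainly among outpatients) and a slightly narrower sample of people without recent CPR training. Because the question is asked before allocation, it cannot bias the comparison between arms.

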2.5 Participant identification / Screening

Potential participants will be identified and approached at research sites. Potential sources of participants include NHS administrative and ancillary staff, patients waiting for outpatient appointments, and hospital visitors.

Different approaches are envisaged for different groups of people.

Trust staff will be informed that the study is taking place by email, and administrative offices will be visited to provide study information. Staff will be notified when they can undertake the CPR quality assessment. On arriving to undertake the CPR quality assessment, eligibility will be assessed and they will be asked to sign the informed consent form.

For other groups, research staff will identify an appropriate location to undertake the CPR quality assessment on recruitment days. People passing by or waiting in the nearby area will be approached and informed that the study is being undertaken. Staff may also be recruited by this route.

Any member of research staff that has delegated authority by the principal investigator may assess participant eligibility.

2.6 Informed consent

Potential participants will be provided with a brief verbal explanation of the study by a member of the research team at the hospital site. A copy of the written participant information sheet will be provided. The potential participant will be given adequate time to review the information and ask questions. In view of the nature of the study, it is anticipated that this decision will be made quickly. If the participant is willing to participate, they will complete a signed consent form.

Written consent will be obtained prior to undertaking any study procedure.

The participant may withdraw at any time without giving reasons and without prejudice to any NHS treatment.

The receipt of written informed consent may be undertaken by any member of research staff that has been delegated authority by the principal investigator. The principal investigator retains overall responsibility for informed consent at their site and must ensure that any person delegated responsibility to participate in the informed consent process is duly authorised, trained and competent.

2.7 Randomisation

2.7.1 Randomisation

Participants will be individually randomised in a 1:1:1 ratio to receive one of the following terminologies:

1. Press at least 5cm
2. Press approximately 5cm
3. Push hard and fast

Participants will be randomised strictly sequentially as participants are eligible for randomisation.

An internet-based randomisation system will be used to randomly assign participants to groups. Details of how to access the service will be provided to sites in a trial specific working instruction

2.7.2 Post-randomisation withdrawals

Participants may withdraw from the study at any time without giving a reason. In view of the nature of the study (no follow-up), we expect such events to be rare.

Where a participant withdraws from the study, research staff will discuss with the participant whether they agree to the retention of data already collected.

2.8 Trial treatments / intervention

2.8.1 Trial treatment(s) / intervention

Randomisation and the CPR quality assessment will take place as soon as possible after written informed consent has been obtained.

The CPR quality assessment will consist of a simulated cardiac arrest. On entering the simulation area, participants will be presented with a standardised scenario. They will be informed that they have entered a room at their local community centre and found a 70-year old male collapsed on the floor. They will be informed that they have phoned 999 and provided the location of the event and that the ambulance is en-route. The 999 operator will then guide the participant as to how to commence CPR using a standardised script. We will use a standardised script, based on that used by UK Ambulance Services to direct the dispatcher-assisted CPR. The only difference between the scripts will be the wording to describe the target chest compression depth. All participants will be directed to deliver compression-only CPR.

The instructions will be delivered using a pre-recorded audio recording. The participant will not have the opportunity to ask questions. If a question is asked, the researcher in the room will respond that the participant should follow the instructions on the audio recording

Each participant will deliver chest compressions for approximately two minutes following the delivery of the first chest compression.

After the scenario, the researcher will provide feedback on the participant's performance, based on their subjective assessment of performance.

2.8.2 Compliance/contamination

In view of the nature of the trial, we expect high compliance.

Participants will be asked to not discuss details of the study with other potential participants to minimise the risk of contamination.

2.9 Blinding

2.9.1 Methods for ensuring blinding

It will not be possible to blind research staff or participants to the CPR instruction terminology. Researchers extracting CPR quality data (i.e. outcome assessors) will be blinded to study intervention.

2.9.2 Methods for unblinding the trial

Only the outcome assessor will be blinded to study allocation. As such, a mechanism for unblinding the participant or any other person is not required.

2.10 End of trial

The trial will end when all required participants have completed the CPR quality assessment.

The trial will be stopped prematurely if:

- Mandated by the Ethics Committee, or,
- Funding for the trial ceases.

The Research Ethics Committee will be notified in writing on completion of the trial.

3. METHODS AND ASSESSMENTS

3.1 Schedule of delivery of intervention and data collection

The schedule of delivery of the intervention and data collection is detailed in table one.

Table 2: Schedule of events

Visit	1	2
Visit Window		Immediately after randomisation
Informed consent	✓	
Inclusion/exclusion criteria	✓	
Demographic information*	✓	
CPR quality assessment		✓
Adverse events	✓	✓
*- Demographic information will include key variables, such as age, gender, height, weight, previous CPR training, previous resuscitation use.		

